- Dose escalation can be achieved by evaluating a higher dose level with the same infusion duration (eg, 800 μ g/day for 14 days to 1600 μ g/day for 14 days), or by evaluating the same dose level with a prolonged infusion duration (eg, from 800 μ g/day for 14 days to 800 μ g/day for 28 days). The DLRT may also decide to explore in parallel both options mentioned above after the dose escalation decision is made, or to prioritize one schedule. In this case, 2 TPI models may be run in parallel to obtain dose recommendations for these 2 schedules separately.
- Intermediate dose levels not pre-specified may be considered based on the optimal dose recommended by the TPI model.

The Amgen Medical Monitor (or EDL) and Amgen Global Safety Officer can make dose decisions without convening the DLRT in the following limited circumstances:

- If a cohort has at least 3 DLT-evaluable subjects and 1 subject experiences a DLT, then the Amgen Medical Monitor and Amgen Global Safety Officer may decide to expand the number of subjects treated in this cohort.
- The Amgen Medical Monitor (or EDL) and Amgen Global Safety Officer may decide to open the next cohort using a de-escalated dose (de-escalated from the dose level of the most recent cohort), if this de-escalated dose had been previously evaluated by the DLRT.

For a full description of statistical analysis methods, please refer to [Section 10](#).

Sponsor: Amgen, Inc.

* Depending on the safety data from the 6400 µg/day cohorts, a level of 12800 µg/day can be added, if agreed by the DLRT. The longest schedule allowing highest dose intensity (14-day or 28-day infusion) found to be tolerated will be selected for the additional cohort.

cIV = continuous intravenous; d = day; DLRT = dose level review team; DLT = dose-limiting toxicity; MTD = maximum tolerated dose; TPI = toxicity probability interval

Study Glossary

Abbreviation or Term	Definition/Explanation
ALP	Alkaline phosphatase
ALT	Alanine aminotransferase
ANC	Absolute neutrophil count
AST	Aspartate aminotransferase
AUC	Area under the concentration-time curve
AUC _{inf}	Area under the concentration-time curve from time zero to infinity
BiTE®	Bispecific T-cell engager
BLQ	Below limit of quantification
C _{24 hr}	Plasma concentration observed after 24 hours
CD	Cluster of differentiation
CEA	Carcinoembryonic antigen
CEACAM	CEA-related cell adhesion molecule
CI	Confidence interval
cIV	Continuous intravenous
CL	Systemic clearance
C _{max}	Maximum plasma concentration

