3. EXPERIMENTAL PLAN

3.1 Study Design

This is a multi-center, open-label, sequential dose-escalation study evaluating AMG 211 as a cIV infusion in adult subjects who have relapsed/refractory GI adenocarcinoma. This study will be conducted in two parts:

- Dose-escalation:
The dose-escalation will define the MTD, safety, tolerability, PK, and pharmacodynamics (PD) of AMG 211.
- Dose-expansion:
The dose-expansion will enroll additional subjects to gain further clinical experience with AMG 211.

Dose-escalation:

In dose-escalation cohorts, the planned dose levels are as follows: 200, 400, 800, 1600, 3200, and 6400 μ g/day. Alternative dose levels up to 12800 μ g/day will be explored in either 14-day or 28 day schedule based on emerging data. See [Section 6.2.1](#) for complete information.

Subjects in cohort 1 of the dose-escalation cohorts will receive AMG 211 for 7 days followed by 21 days off treatment (cycle 1). After completing cycle 1, if no DLTs are observed, all subjects in cohort 1 will be allowed to continue treatment with the same

dose of AMG 211, but the infusion duration will be 14 days followed by 14 days off treatment.

In the subsequent dose-escalation cohorts, AMG 211 will be administered at escalating doses in a 2 weeks on and 2 weeks off schedule. Based on the results, the Dose Level Review Team (DLRT) may choose to extend the infusion duration from 14 to 28 days (a 4 weeks on and 2 weeks off schedule) if the 14-day administration schedule has been well tolerated and the safety profile allows for a longer infusion duration, and no anti-tumor response has been observed in a 14-day administration schedule. Moreover, the DLRT may decide to enroll in parallel into a cohort with a 28-day treatment duration or to prioritize one infusion schedule.

Dose escalation decisions will consider the incidence of DLTs among DLT-evaluable subjects.

The DLRT may consider the dose escalation complete if 1 of the following rules is met:

- The highest planned dose level is evaluated and no DLTs occur at any dose level. In this case the maximum administrated dose will be used in a dose-expansion cohort
- The toxicity probability interval (TPI) Bayesian model recommends the same dose 3 times (not necessarily sequentially)
- A total of approximately 39 DLT-evaluable subjects have been enrolled

Dose-Expansion:

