Approximately 39 subjects will be enrolled in the dose-expansion cohort to gain further clinical experience with AMG 211. Of those, approximately 29 subjects will concurrently participate in the Imaging Study. Multiple dose levels will be evaluated in the dose-expansion cohort. Subjects not participating in the Imaging Study will start enrollment into the dose-expansion cohort upon completion of the dose-escalation cohorts and will be treated using the MTD or recommended phase 2 dose. Subjects concurrently participating in the Imaging Study may start enrollment into the dose-expansion cohort while dose-escalation cohorts are still open for enrollment and will be treated at the MTD or recommended phase 2 dose or at a lower dose. [Table 3](#) presents an overview of the study design.

Table 3. Study Design Overview

Part	Cohort	Dose Level	Number of Subjects
Dose Escalation ^b	1	200 µg/d for 7 days in cycle 1 200 µg/d for 14 days in cycle 2 and all subsequent cycles	3-6
	2	200 µg/d for 14 days in all cycles	3-6
	3	400 µg/d for 14 days in all cycles	3-6
	4	800 µg/d for 14 days in all cycles	3-6
	5	1600 µg/d for 14 days in all cycles	3-6
	6	3200 µg/d for 14 days in all cycles	3-6
	7	6400 µg/d for 14 days in all cycles	3-6
	8*	12800 µg/d for 14 or 28 days in all cycles	3-6
28-day Schedule	X-1 ^a	Dose Level -1 of 14-day Schedule × 28 days	3-6
	X-2 ^a	MTD × 28 days	3-6
Dose Expansion	A	MTD or lower dose or highest dose tested without reaching MTD	39

d = day; DLT = dose-limiting toxicity; DRLM = dose level review meeting; EC₅₀ = 50% of the maximal effective concentration level; MTD = maximum tolerated dose; PD = pharmacodynamic; PK = pharmacokinetic

^a Alternative dosing regimens (eg, 28-day infusions) may be explored after a DRLM decision based on 1) occurrence of DLT(s) or other emerging safety data; 2) PK/PD data demonstrating drug exposure that is in the range or above the mean EC₅₀ concentration of 29 ng/mL; 3) absence of objective responses in the 14-day infusion schedule

^b Approximately 6 subjects from the dose escalation cohorts will concurrently participate in the Imaging Study after completion of cycle 2 of cIV AMG 211 treatment.

* Alternative dose level up to 12800 µg/day will be explored in either 14-day or 28-day schedule based on emerging data.

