6.2.1.1 Dosage, Administration, and Schedule

AMG 211 will be delivered using preprogrammed infusion pumps approved for use by the appropriate regulatory authority for the country in which the subject is undergoing treatment.

AMG 211 infusion for solution will be prepared in bags for IV infusion. The investigational product will be administered as a cIV infusion at a constant flow rate over 1 to 4 weeks followed by a 3-week (cohort 1 in the dose-escalation cohorts) or 2-week

(all other cohorts) treatment free interval prior to the following treatment cycle. Subjects will be hospitalized on day 1 cycle 1 for a minimum of 72 hours and at all subsequent cycles for a minimum of 48 hours. Subjects can be hospitalized for a longer time period at the discretion of the investigator. If required for logistical reasons (eg, long travel times), subjects may be hospitalized the day before dosing (day -1) of any cycle and at the EOI for cycle 1 for required PK samples. Subjects in the 7- and 14-day schedules will receive AMG 211 for 7 or 14 days followed by 21 days off or 14 days off, respectively (a 28-day cycle). Subjects on a 28-day schedule will receive AMG 211 for 28 days followed by 14 days off (a 42-day cycle).

The planned dose levels for the dose-escalation cohorts are: 200, 400, 800, 1600, 3200, and 6400 µg/d. Alternative dose levels up to 12800 µg/day will be explored in either 14-day or 28-day schedule based on emerging data. The MTD or recommended phase 2 dose will be administered in the dose-expansion cohort.

The infusion start time should be chosen carefully to avoid any interference or inconvenience with time points of safety assessments, PK/PD measurements, and infusion bag changes. The site should record any unscheduled interruption of an infusion on the eCRF, and provide the start and stop date/time of the infusion and the bag change.

AMG 211 should be administered through a central venous access. In the event that administration through a central venous access is not possible, AMG 211 may be administered temporarily through a peripheral venous line if the subject is hospitalized. The final solution for infusion should be administered through a 0.2 µm in-line filter.

Administration of the premedication (eg, dexamethasone) to minimize the risk of cytokine-release syndrome symptoms is recommended for all treatments at a dose of 800 µg/day or higher (see [Section 6.5](#)).

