10.3.1 Interim Analyses

The DLRT (see [Section 10.3.2](#)) is responsible for all dose level decisions during dose escalation. Dose decisions are planned after every 3 to 6 subjects are enrolled throughout the dose-escalation cohorts. The DLRT considers the recommendation for subsequent doses based on the following rules:

- Based on the modified TPI Bayesian model, the next dose is the one with the highest probability of the target TPI (0.20, 0.35), but with a less than 0.25 probability of an excessive or unacceptable TPI.
- If ≥ 1 subject has a DLT at a dose level, then dose escalation cannot occur unless there are 6 or more DLT-evaluable subjects at that dose level. However, if a transient cytokine-release syndrome is reported as the DLT, but resolves within

48 hours and can be managed with prophylactic corticosteroids, the DLRT may decide to escalate the dose with the institution of prophylactic corticosteroid administration.

- The maximum allowed dose increase will be 1 dose level above the maximum of previous evaluated doses.
- Dose escalation can be achieved by evaluating a higher dose level with the same infusion duration (eg, 800 µg/day for 14 days to 1600 µg/day for 14 days), or by evaluating the same dose level with a prolonged infusion duration (eg, from 800 µg/day for 14 days to 800 µg/day for 28 days). The DLRT may also decide to explore in parallel both options mentioned above after the dose-escalation decision is made, or to prioritize one schedule. In this case, 2 TPI models may be run in parallel to obtain dose recommendations for these 2 schedules separately.
- Intermediate dose levels not pre-specified may be considered based on the optimal dose recommended by the TPI model.

The DLRT is responsible for making the decision to end dose escalation. Generally, the DLRT may consider the dose escalation complete if 1 of the following rules is met:

- The highest planned dose level is evaluated and no DLTs occur at any dose level. In this case the maximum administered dose will be used in a dose-expansion cohort.
- The TPI Bayesian model recommends the same dose 3 times (not necessarily sequentially).
- A total of approximately 39 DLT-evaluable subjects have been enrolled.

The Amgen Medical Monitor and Amgen Global Safety Officer can make dose decisions without convening the DRLT in the following limited circumstances:

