Appendix E. Toxicity Probability Interval (TPI) Bayesian Design

The dose-escalation cohorts will use a TPI Bayesian design to guide dose escalation. The MTD target TPI for DLT is (0.20, 0.35), and TPIs of (0.35, 0.60) and (0.60, 1.00) are defined as excessive and unacceptable, respectively. The design seeks to identify a dose most likely to have a DLT rate in the target TPI, but with overdose control that limits the possibility that the dose has an excessive or unacceptable DLT rate (Babb et al, 1998). The probability of a DLT at dose level d_i is assumed to follow a Bernoulli distribution with probability p_i where the logit of p_i increases linearly with the log of the standardized dose in the following 2-parameter logistic model:

$$\log [p_i / (1-p_i)] = \text{logit}(p_i) = \log[a] + \exp(\log[b]) \log (d_i / d_{\max})$$

where a and b are random variables and d_{\max} is the maximum planned dose.

A minimally informative prior distribution (Neuenschwander et al, 2008) was selected for $\theta = (\log a, \log b)$ where the probability that the true DLT rate is ≤ 0.60 at the lowest dose (200 $\mu\text{g}/\text{day}$ for 7 days) is 0.90 and the probability the true DLT rate is ≤ 0.20 at the maximum dose (6400 $\mu\text{g}/\text{day}$ for 14 days) is 0.21. Median values for p_i were interpolated per the logistic model. For each d_i , 2 quantiles for p_i were selected from a Beta distribution with the target median and a precision < 2 . This set of quantiles fully specified a target prior for θ . A bivariate normal distribution for θ was assumed where $(\log a)$ has a normal distribution with mean ma and standard deviation sa , and $(\log b)$ has a normal distribution with mean mb and standard deviation sb , and r is the correlation between $(\log a)$ and $(\log b)$. Numerical integration was used to calculate $\Pr[p_i \leq q(d_i)]$, where $q(d_i)$ is a quantile for dose d_i . An optimal bivariate normal distribution was estimated that achieved the minimum sum of squared difference between achieved and specified quantiles across all doses. The bivariate normal distribution prior solution has $ma = 0.0536$, $sa = 1.685$, $mb = -0.1469$, $sb = 1.001$, and $r = -0.216$.

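### Appendix E was not updated for the higher escalation cap and the conditional 12800 µg/day cohort: its simulation table matches the earlier design, and its documented model puts 12800 above the 0.25 overdose limit at the Table 3 cohort sizes tested.

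*Protocol*

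**What the plan says.** **The model.** Protocol Appendix E uses a two-parameter logistic model in log(dose/d_max), where d_max "is the maximum planned dose". The next paragraph sets the prior by two anchors: a 0.90 probability that the DLT rate is at most 0.60 at 200 µg/day, and a 0.21 probability that it is at most "0.20 at the maximum dose (6400" µg/day for 14 days).

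**The doses.** Section 3.1 says "the planned dose levels are as follows: 200, 400, 800, 1600, 3200, and 6400" µg/day. Table 3 adds a starred cohort 8 at 12800 µg/day "for 14 or 28 days in all cycles". On levels up to 12800, section 6.2.1.1 says they "will be explored in either 14-day or 28-day schedule based on emerging data". The schema footnote is softer: a level of 12800 µg/"day can be added, if agreed by the DLRT".

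**The rule.** Section 10.3.1 takes as next dose the one with the highest probability of the target interval (0.20 to 0.35), "but with a less than 0.25 probability of an excessive or unacceptable TPI". It also says: "Intermediate dose levels not pre-specified may be considered based on the optimal dose recommended by the TPI model". Escalation may be considered complete at about 39 DLT-evaluable subjects.

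**The simulation.** Section 10.2 refers to Appendix E for average sample size and other operating characteristics. Appendix E says the simulated doses were chosen under the rules of section 10.3.1. SAP Appendix C prints the same table, with SAP section 8 as its rule source, where the cap is about 24. SAP section 1 ties the SAP to the protocol dated 24 March 2014.

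**The concern.** The dose range, the cap and the schedules have moved, and the appendix that specifies the escalation model has not. Appendix E does not mention 12800, and the Amendment 3 description of changes lists no change to it.

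Two consequences matter. A reader sent from section 10.2 to Appendix E will take the tabulated sample sizes, selection rates and DLT rates as properties of the present design. And when the review team asks the model about cohort 8, the output turns on a scaling constant the protocol does not give as a number. If the model rule and the cohort table disagree, the team should know that it is overriding the rule and on what grounds.

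**Working it through.** **1. Which d_max does the printed prior belong to?**
Inputs (Appendix E): log a has mean 0.0536 and SD 1.685; log b has mean −0.1469 and SD 1.001; correlation −0.216. The model is logit(p) = log a + b·log(d/d_max).

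At d = d_max the second term is zero. With d_max = 6400, therefore, P(p ≤ 0.20 at 6400) = Φ((−1.3863 − 0.0536)/1.685) = Φ(−0.855) = 0.196. The other values come from numerical integration over the prior.

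| Anchor | Stated | d_max 6400 | d_max 12800 |
|---|---|---|---|
| P(p ≤ 0.60) at 200 | 0.90 | 0.900 | 0.916 |
| P(p ≤ 0.20) at 6400 | 0.21 | 0.196 | 0.379 |

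The prior was a least-squares fit, so 0.196 against 0.21 is close enough. Only 6400 fits.

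**2. Overdose probability at 12800 with d_max = 6400.**
The posterior is the prior times the binomial likelihood with 0 DLTs. Overdose means p > 0.35 (excessive plus unacceptable). The protocol reports about 32 subjects without a DLT (section 2.2.4) but gives neither the split by dose nor the number DLT-evaluable, so the splits are assumptions. Cohorts 1 and 2 are pooled at 200, and schedules are pooled by daily dose.

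Split A has 6 at 200, 3 each at 400, 800 and 1600, and 5 at 3200:

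| DLT-free at 6400 | P(p > 0.35) at 12800 |
|---|---|
| 3 | 0.454 |
| 4 | 0.417 |
| 6 | 0.360 |
| 13 | 0.251 |
| 14 | 0.242 |

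Sixteen combinations were also run: 3 or 6 in each cohort up to 1600, 3 or 6 at 3200, and 3 to 6 at 6400. They ranged from 0.36 to 0.48, and none met 0.25. With 3 rather than 5 at 3200, the limit is first met at 13 subjects at 6400 (12: 0.257; 13: 0.247). That is 6 + 9 + 3 + 13 = 31 subjects in total; under split A it is 6 + 9 + 5 + 14 = 34. Both are below 39, but both need more than the 3 to 6 per cohort in Table 3.

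Under split A with 6 at 6400, the target-interval probability is 0.190 at 12800 and 0.096 at 6400. Of those two doses, 12800 scores higher on the target interval, so it is the overdose limit that rules it out.

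**3. Intermediate level and 6400 itself (d_max = 6400).**
Under split A with 6 at 6400, P(p > 0.35) at 9600 is 0.21, which meets the limit. With 3 at 6400 it is 0.31, which does not. Before 6400 is opened, P(p > 0.35) at 6400 is 0.27 with 3 subjects at 3200 and 0.24 with 5.

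**4. Effect of moving d_max while keeping the prior.**
Under split A, 12800 goes from 0.454 to 0.267 with 3 at 6400, and from 0.360 to 0.221 with 6. The first ratio is 0.267/0.454 = 0.59 and the second 0.221/0.360 = 0.61, a cut of about two fifths.

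**5. The simulation table.**
The protocol and SAP tables agree in every entry, including mean sample size (15.7 and 20.8), acceptable-dose rate (83.1% and 51.4%), no-dose rate (4.5% and 3.7%) and DLT rate (24.1% and 15.0%). The printed intervals match exact binomial intervals for 1000 runs (831/1000 gives 80.6% to 85.4%). Cohort size was fixed at 3, neither scenario puts its target dose above 3200, and no 12800 level or 28-day model is described. The runs cannot be repeated exactly because the scenario distributions are not given.

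**The case against.** **d_max is not really open.** This largely stands. The planned list ends at 6400, 12800 is called an alternative level, and Appendix E names 6400 as the maximum dose beside the formula. A reader might infer two readings of equal rank; the documents do not support that, because 12800 contradicts the stated anchor. What remains is that the constant is unstated while Table 3 lists a higher dose.

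**The protocol leaves room.** This also stands. The review team considers the model's recommendation rather than being bound by it. Cohort 8 is conditional, the text says up to 12800, and intermediate levels and cohort expansion are allowed. A reader might infer that the model forbids 12800; it does not.

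**The strictness predates the added cohort.** Partly true. The limit is missed at 6400 itself with 3 subjects at 3200, so the original prior contributes.

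**The no-DLT case may not use the model.** SAP Appendix D lists the model plot for review meetings only if a DLT has occurred. That lowers the practical weight, but section 10.3.1 does not make the 0.25 rule depend on a DLT.

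**Schedules may be modelled separately.** Section 10.3.1 permits two parallel models, so pooling is an assumption here.

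**On the simulation**, the High-scenario upper quartile of 24 equals the SAP cap, and a reader might infer that the cap cut off a quarter of the runs. It shows only that at least a quarter reached 24; with cohorts of 3, a run can stop there under the same-dose-three-times rule. Section 10.2 also calls the escalation sample size empirical, so the table does not justify the 39.

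**Conclusion.** The concern holds in two parts.

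The firmer part is the simulation table. It is presented as following current section 10.3.1, yet it is identical to results produced under an earlier cap and dose range. It cannot be assumed to describe the present design. This needs no modelling assumption.

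The second part is a conflict between cohort 8 and the 0.25 rule under the model that the documents support. P(DLT rate > 0.35) at 12800 is about 0.36 to 0.48, and about 13 or 14 DLT-free subjects at 6400 are needed to meet the limit. This rests on d_max = 6400, zero DLTs, assumed splits and pooling by daily dose. Confidence attaches to the direction, not to any one probability or to the exact crossing point, which moves with the number at 3200.

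Changing d_max to 12800 on the same prior would lower these probabilities by about two fifths, enough to reverse the decision for some splits. It should not happen silently.

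A reader might also infer that the SAP needs a numeric d_max. It does not: its dose list stops at 6400, so the value is clear there.

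**What to change.** - In protocol Appendix E, state d_max as a number and say how a 12800 level enters the model.
- Reconcile the 12800 passages (Table 3, the schema footnote, sections 3.1 and 6.2.1.1) with the 0.25 rule in section 10.3.1. No view is taken here on which dose or rule is right.
- Label the simulation table, and the reference to it in section 10.2, as describing the original design. Alternatively, re-run it for the current dose range, schedules and cap. Labelling is sufficient.
- If the prior or d_max is changed, disclose that the change follows about 32 subjects without a DLT, and show the dose decision under the original prior as well.

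The cost is a few sentences in Appendix E, section 10.2 and the dose passages if the table is relabelled, and a few days of simulation if it is re-run.

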Appendix F. Karnofsky Performance Status and Definitions

Karnofsky Performance Status	
Score	Description
100%	Normal; no complaints; no evidence of disease
90%	Able to carry on normal activity; minor signs or symptoms of disease
80%	Normal activity with effort; some signs of symptoms of disease
70%	Cares for self; unable to carry on normal activity or to do active work
60%	Requires occasional assistance, but is able to care for most of his needs
50%	Requires considerable assistance and frequent medical care
40%	Disabled; requires special care and assistance
30%	Severely disabled; hospitalization is indicated although death not imminent
20%	Very sick; hospitalization necessary; active support treatment necessary
10%	Moribund; fatal processes progressing rapidly
0%	Dead

Adapted from [Karnofsky et al, 1948](#).

